- 17) Women found to be pregnant by a pregnancy test performed within 14 days before registration.
- 18) Women who may need to breastfeed during the study period and for 25 days after the last dose of the study drug.
- 19) Patients who are otherwise considered ineligible for the study in the opinion of the investigators (investigator or subinvestigator).

Dosage form, dose and route of administration:

<Dosage form>

White film-coated tablets, each of which contains 20 mg AC220, or yellow film-coated tablets, each of which contains 30 mg AC220.

<Regimen>

Quizartinib will be administered at an initial dose of 30 mg/day. For patients receiving strong cytochrome P450 (CYP) 3A4 inhibitors, an initial dose of 20 mg/day will be used. Quizartinib will be orally administered once daily every morning. Treatment with quizartinib will be administered in

28-day cycles and continued until the withdrawal criteria are met.

If a patient vomits after taking a dose of the study drug, a replacement dose may not be given on the same day. A patient who did not take the study drug at the usual hour of dosing (eg, forgot to take the dose) will be allowed to take the missed dose within 10 hours after the usual hour of dosing (for example, if the patient usually takes the drug at 7:00 or 8:00, he/she may take it by 17:00 or 18:00). In this case, the next dose of the study drug on the following day should be taken at least 12 hours after the time when the last dose was taken. If the patient does not take the missed dose by 10 hours after the usual hour of dosing, he/she should not take the study drug on that day and resume taking the drug on the following day. The patient may not take two doses at once on the day when the drug is resumed.

<Criteria for dose increase of the study drug>

The dose of quizartinib will be increased in accordance with the following criteria. A 12-lead ECG will be measured at least once weekly for the first 2 weeks after a dose increase to confirm the presence or absence of QTcF prolongation after the dose increase. When doing this, triplicate ECG recordings will be obtained.

Assessment criteria for dose increase on Day 16 of Cycle 1
Patients not concomitantly using strong CYP3A4 inhibitors:
The dose of quizartinib will be increased to 60 mg/day if all
QTcF data (determined as the average of three measurements)
taken by Day 15 of Cycle 1 are 450 ms or shorter.

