## 5.2.4.3 Criteria for Dose Increase of the Study Drug

If the patient's condition satisfies the following criteria on Day 16 of Cycle 1 or Day 1 of Cycle 2 (or thereafter), the dose of quizartinib will be increased according to Table 5.2-2. A 12-lead ECG will be measured at least once weekly for the first 2 weeks after a dose increase to confirm the presence or absence of QTcF prolongation after the dose increase. When doing this, triplicate ECG recordings will be obtained. The dose of quizartinib should not exceed 60 mg/day throughout the study period (30 mg/day for patients concomitantly using strong CYP3A4 inhibitors).

Table 5.2-2 Method of Dose Increase of Quizartinib

Dose	One level Increased Dose
20 mg/day	30 mg/day
30 mg/day	60 mg/day
60 mg/day	No dose increase

### Assessment criteria for dose increase on Day 16 of Cycle 1

Patients not concomitantly using strong CYP3A4 inhibitors:

The dose of quizartinib will be increased to 60 mg/day if all QTcF data (determined as the average of three measurements) taken by Day 15 of Cycle 1 are 450 ms or shorter.

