## Patients concomitantly using strong CYP3A4 inhibitors:

The dose of quizartinib will be increased to 30 mg/day if all QTcF data (determined as the average of three measurements) taken by Day 15 of Cycle 1 are 450 ms or shorter. A list of CYP3A4 inhibitors is provided in Appendix 4.

If treatment with quizartinib is interrupted by Day 16 of Cycle 1, whether to increase the dose or not will be determined in accordance with the following criteria.

- Interruption of treatment for 2 days or shorter: The dose may be increased on Day 16 of Cycle 1.
- Interruption of treatment for 3 to 6 days: Consult with the sponsor's medical monitor etc. and assess whether to increase the dose or not on Day 16 of Cycle 1.
- Interruption of treatment for 7 days or longer: The dose will not be increased on Day 16 of Cycle 1. Decide whether to increase the dose or not on Day 1 of Cycle 2 or later.

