### Assessment criteria for dose increase on Day 1 of Cycle 2 or later

For patients who have not achieved CR, CRp, or CRi after at least 1 cycle of treatment with quizartinib\* and whose condition before the decision on dose increase satisfies the following requirements, the dose of quizartinib will be increased.

- Absence of Grade 3 or more severe treatment-related non-hematological toxicity
- 60 ms or shorter increase in QTcF interval from baseline
- Absence of hypoplastic bone marrow upon the decision of a dose increase
- \* At least 1 cycle of treatment with quizartinib: Treatment with quizartinib is given for at least 13 consecutive days

For patients who have relapsed after achieving CR, CRp, CRi, or PR, and satisfy the assessment criteria for dose increase on Day 1 of Cycle 2 or later, the dose of quizartinib may be increased. The dose will be increased to 60 mg/day if strong CYP3A4 inhibitors are not concomitantly used, and to 30 mg/day if strong CYP3A4 inhibitors are concomitantly used.

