### 5.4.2 Non-hematological Toxicity

If a quizartinib-related Grade 3 or more severe non-hematological toxicity does not improve to Grade 2 or less severe, and it persists for at least 48 hours, treatment with quizartinib should be interrupted for a maximum of 14 days when quizartinib has been administered at a dose of 30 mg/day or 60 mg/day. If the toxicity recovers to Grade 1 or less severe within 14 days after the onset, treatment with quizartinib may be resumed at a reduced dose. When quizartinib is administered at a dose of 20 mg/day, treatment with quizartinib should be discontinued.

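### In an uninterrupted patient the Day 16 dose increase depends on QTcF alone, so as written it applies during an ongoing related Grade 3 or worse non-hematological toxicity that has not yet lasted 48 hours

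*Combined protocol and SAP*

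**What the plan says.** Section 5.2.4.3 has two sets of criteria for raising the dose.

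- **Day 16 of Cycle 1.** Without a strong CYP3A4 inhibitor, "The dose of quizartinib will be increased to 60 mg/day if all QTcF data" taken by Day 15 are 450 ms or shorter. With one, "The dose of quizartinib will be increased to 30 mg/day if all QTcF data" meet the same limit. The Protocol Synopsis repeats the rule ("The dose of quizartinib will be increased to 60 mg/day if all"). The only other Day 16 provisions concern patients whose treatment was interrupted beforehand, for example: "Interruption of treatment for 2 days or shorter: The dose may be increased on Day 16 of Cycle 1". After 3 to 6 days off drug the medical monitor is consulted; after 7 or more days there is no increase.
- **Day 1 of Cycle 2 or later.** The increase applies "For patients who have not achieved CR, CRp, or CRi after at least 1 cycle of treatment", subject to three requirements. One is a limit on QTcF change from baseline. The others are "Absence of Grade 3 or more severe treatment-related non-hematological toxicity" and "Absence of hypoplastic bone marrow upon the decision of a dose increase".

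Section 5.4.2 requires interruption (discontinuation at 20 mg/day) when a related Grade 3 or worse non-hematological toxicity "does not improve to Grade 2 or less severe, and it persists for at least 48 hours". Section 5.4 and Table 5.4-1 set the one-level reductions: 60 to 30 and 30 to 20 mg/day.

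**The concern.** The Day 16 wording is mandatory and looks only at QTcF. The same section treats a related Grade 3 or worse non-hematological toxicity as a bar to escalation one visit later. The rationale for the Day 16 step in Section 3.2.2 discusses steady-state exposure and QTc, and gives no reason for leaving other toxicity out.

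What is at stake is the safety of individual patients. A 30 mg starter has the dose doubled while the event is unresolved.

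- If the event then reaches 48 hours, the patient has taken one or two doses at 60 mg before interruption. The one-level reduction allows resumption, after recovery to Grade 1 or less, at 30 mg/day, the dose on which the event began. Without the increase the reduced dose would have been 20 mg/day.
- If the event eases to Grade 2 or less before 48 hours, Section 5.4.2 is not triggered and the patient stays at 60 mg/day.

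**Working it through.** **Rule trace.** Take an uninterrupted patient with every averaged QTcF at 450 ms or shorter, and a related Grade 3 non-hematological event that began less than 48 hours before the Day 16 dose and has not eased. The provisions that might stop the increase are:

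| Provision | Does it block the Day 16 increase? |
|---|---|
| 5.2.4.3, Day 16 criterion | No; it is met |
| 5.2.4.3, interruption clauses | No; they need a prior interruption |
| 5.2.4.3, Cycle 2 toxicity condition | No; it applies from Day 1 of Cycle 2 |
| 5.4.2 | No; 48 hours not reached |
| 5.4.3 | No; it needs a completed cycle and CRp or CRi |
| 5.4.5 | No; it needs a prior dose reduction |
| 3.1 and 5.2.4.1 | No; both refer back to 5.2.4.3 |
| 5.7.1 item 3 | Allows discontinuation, not holding the dose |

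The rule therefore directs the increase. Toxicity that reaches 48 hours before the Day 16 dose is dealt with by Section 5.4.2 and the interruption clauses, and is outside this point.

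**How many patients.** The plan states no figure to reproduce and gives no event rate. Dosing is once daily in the morning (Section 5.2.4.2), so 15 days separate the first dose from the Day 16 dose, and the window is the last 2 of them. With uniform onset the share of events starting in the window is w = 2/15 = 13%. All remaining inputs are assumptions:

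- r, the share of patients with a related Grade 3 or worse non-hematological event before Day 16: 5% to 20%
- o, the share of window events still Grade 3 or worse at the Day 16 dose: 50% to 100%
- q, the share of these patients who pass the QTcF rule: 70% to 100%

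The per-patient probability is p = r × w × o × q. The expected number is 41p, and the chance of at least one affected patient is 1 − (1 − p)^41.

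| r | o | q | Expected of 41 | Chance of at least one |
|---|---|---|---|---|
| 5% | 50% | 70% | 0.10 | 9% |
| 5% | 100% | 100% | 0.27 | 24% |
| 10% | 100% | 100% | 0.55 | 42% |
| 20% | 50% | 70% | 0.38 | 32% |
| 20% | 100% | 100% | 1.09 | 67% |

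**Exposure in an affected 30 mg starter.** The half-life is about 3 days (Section 1.2.1.2.5). Assuming one compartment and steady state, the fraction retained per day is k = 2^(−1/3) = 0.794. The post-dose load at 30 mg/day is 30/(1 − k) = 145.4 mg.

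- One 60 mg dose adds 30 mg: 30/145.4 = 21% higher.
- Two add 30(1 + k) = 53.8 mg: 53.8/145.4 = 37% higher.

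The resumption dose is 30 rather than 20 mg/day, a ratio of 1.5.

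**The case against.** The strongest reply is that the investigator is not trapped. Section 9.1 calls for appropriate action on any adverse event, Section 15.4 recognises urgent safety measures, and Section 15.5 excepts immediate hazards from its ban on deviations. A dose can also be withheld briefly, after which the increase becomes optional. A reader might infer that the protocol forces escalation with no way out; the documents do not support that. What remains is that none of these clauses is a Day 16 criterion for staying at the current dose. A skipped dose gives more discretion than an observed Grade 3 event.

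Second, the main known risk is gated. Four of the five dose-limiting toxicities in Study CP0001 were QTc prolongation, and the Day 16 rule sets an absolute QTcF limit that the Cycle 2 rule lacks. No protocol-specified dose-limiting toxicity was seen in nine Japanese patients at 20 to 60 mg/day. The two sets of criteria also serve different purposes. This stands, and it limits the weight of the point. It does not explain why other severe related toxicity should count at one decision and not at the other.

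Third, Section 5.4.2 tolerates Grade 3 events shorter than 48 hours at any dose. That is so, but continuing a dose through a short event differs from doubling it.

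Fourth, the frequency range is wholly assumed. It treats toxicity and passing the QTcF rule as independent, and the event rate should be read as excluding QTc events, since those patients fail the rule. The 67% needs every input at its maximum, so it is not evidence that a case is likely. In the other direction, scheduled laboratory tests before Day 16 fall on Days 1, 2, 8 and 15. Without unscheduled tests, an abnormality arising after Day 8 is first documented about a day before the Day 16 dose, before 48-hour persistence can be shown.

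Fifth, the trial aims to confirm the AC220-007 regimen, whose detailed Day 16 criteria are not in the documents. Section 1.2.1.2.3 says only that increases there rest on safety and efficacy requirements. Whether the added condition matches or departs from that regimen cannot be checked.

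**Conclusion.** The point holds in a narrow form, as a cheap improvement. For an uninterrupted patient, the Day 16 rule as written raises the dose during an ongoing related Grade 3 or worse non-hematological toxicity of under 48 hours, a state that bars escalation from Day 1 of Cycle 2.

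The size is small: roughly 0.1 to 1 of 41 patients, resting on assumed event, persistence and QTcF pass rates and on uniform onset. The exposure figures rest on a one-compartment steady-state assumption.

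Two further inferences would go too far. The primary endpoint definition and the design's error rates are unaffected. The 30 versus 20 mg resumption argument applies only to 30 mg starters; for 20 mg starters Section 5.4.2 works differently.

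**What to change.** Add one condition to the Day 16 criteria in Section 5.2.4.3, for both CYP3A4 groups, and to the synopsis. Take the Cycle 2 item "Absence of Grade 3 or more severe treatment-related non-hematological toxicity" and limit it to toxicity that is ongoing at the decision. Reassess held patients on Day 1 of Cycle 2 or later under the existing criteria. A sentence giving Section 5.4 precedence over 5.2.4.3 would be an optional clarification.

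The cost is a short amendment and a site memo. The downsides are:

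- A held patient stays at the starting dose for at least the rest of Cycle 1, nominally Days 16 to 28 (13 days), although Section 3.2.2 regards 60 mg as likely superior.
- A held patient in CR, CRp or CRi at Day 1 of Cycle 2 is not escalated then, and might never be unless relapse brings the dose back into question. In the earlier study's 30 mg group 24 of 38 had not reached CRc after Cycle 1, so up to 14/38 = 37% of held patients might miss the increase for this reason: 0.10 × 0.37 = 0.04 to 1.09 × 0.37 = 0.4 of 41 patients. Hypoplastic marrow has the same effect, but the documents give no rate for it.
- A held 20 mg starter whose toxicity reaches 48 hours is discontinued under Section 5.4.2. After escalation to 30 mg the same section would have allowed interruption and possible resumption. The amendment should acknowledge this difference.

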## Patients concomitantly using strong CYP3A4 inhibitors:

The dose of quizartinib will be increased to 30 mg/day if all QTcF data (determined as the average of three measurements) taken by Day 15 of Cycle 1 are 450 ms or shorter. A list of CYP3A4 inhibitors is provided in Appendix 4.

If treatment with quizartinib is interrupted by Day 16 of Cycle 1, whether to increase the dose or not will be determined in accordance with the following criteria.

- Interruption of treatment for 2 days or shorter: The dose may be increased on Day 16 of Cycle 1.
- Interruption of treatment for 3 to 6 days: Consult with the sponsor's medical monitor etc. and assess whether to increase the dose or not on Day 16 of Cycle 1.
- Interruption of treatment for 7 days or longer: The dose will not be increased on Day 16 of Cycle 1. Decide whether to increase the dose or not on Day 1 of Cycle 2 or later.

### Assessment criteria for dose increase on Day 1 of Cycle 2 or later

For patients who have not achieved CR, CRp, or CRi after at least 1 cycle of treatment with quizartinib\* and whose condition before the decision on dose increase satisfies the following requirements, the dose of quizartinib will be increased.

- Absence of Grade 3 or more severe treatment-related non-hematological toxicity
- 60 ms or shorter increase in QTcF interval from baseline
- Absence of hypoplastic bone marrow upon the decision of a dose increase
- \* At least 1 cycle of treatment with quizartinib: Treatment with quizartinib is given for at least 13 consecutive days

For patients who have relapsed after achieving CR, CRp, CRi, or PR, and satisfy the assessment criteria for dose increase on Day 1 of Cycle 2 or later, the dose of quizartinib may be increased. The dose will be increased to 60 mg/day if strong CYP3A4 inhibitors are not concomitantly used, and to 30 mg/day if strong CYP3A4 inhibitors are concomitantly used.

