## 5.4 Dose Interruptions and Reductions

If any of the criteria in Section 5.4.1 to Section 5.4.4 apply, treatment with quizartinib will be interrupted or the dose of quizartinib will be reduced. The dose of quizartinib will be reduced by one level at a time according to Table 5.4-1. If quizartinib is administered at a dose of 20 mg/day, a further dose reduction is not allowed.

Table 5.4-1 Method of Dose Reduction of Quizartinib

Dose	One level Reduced Dose
60 mg/day	30 mg/day
30 mg/day	20 mg/day
20 mg/day	No dose reduction

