## **5.4.1 QTcF Prolongation**

In case of QTcF prolongation, the dose will be reduced in the following manner.

Table 5.4-2 Criteria for Dose Interruption and Reduction When QTcF Prolongation Occurs during Treatment with Quizartinib at 30 mg/day or 60 mg/day

CTCAE Grade	Method of Dose Reduction		
Grade 2	
 
Reduce the dose by one level. It is not necessary to interrupt treatment.
 
The dose may be increased to the dose before dose reduction if QTcF prolongation recovers to Grade 1 or less severe after treatment at the reduced dose for at least 28 days.
 
		
Grade 3	
 
Interrupt quizartinib treatment for a maximum of 14 days.
 
Resume quizartinib treatment at a one level reduced dose, relative to the dose immediately before the interruption, if the increase in QTcF interval from baseline is 30 ms or shorter or the QTcF interval recovers to 450 ms or shorter within 14 days after the onset.
 
Do not increase the dose after resumption of quizartinib treatment.
 
		
Grade 4	Discontinue quizartinib treatment.		

For the treatment of QTcF prolongation, "9.10.2 Measures Taken in Case of QTcF Prolongation" should be followed.

Table 5.4-3 Criteria for Dose Interruption and Reduction When QTcF Prolongation Occurs during Treatment with Quizartinib at 20 mg/day

CTCAE Grade	Method of Dose Reduction	
Grade 2	
 
Interrupt quizartinib treatment for a maximum of 14 days.
 
Resume quizartinib treatment at a dose of 20 mg/day if QTcF prolongation recovers to Grade 1 or less severe.
 
	
Grade 3	
 
[If strong CYP3A4 inhibitors are concomitantly used]
 
Interrupt quizartinib treatment for a maximum of 14 days.
 
Resume quizartinib treatment at a dose of 20 mg/day if the increase in QTcF interval from baseline is 30 ms or shorter or the QTcF interval recovers to 450 ms or shorter within 14 days after the onset, and the concomitant use of strong CYP3A4 inhibitors is discontinued.
 
Do not increase the dose after resumption of quizartinib treatment.
 
[If strong CYP3A4 inhibitors are not concomitantly used]
 
Discontinue quizartinib treatment.
 
	
Grade 4	Discontinue quizartinib treatment.	

For the treatment of QTcF prolongation, "9.10.2 Measures Taken in Case of QTcF Prolongation" should be followed.

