#### 5.4.5 Dose Increase after Dose Reduction

The dose of quizartinib will be increased by one level at a time in patients whose dose has once been reduced. However, if the dose of quizartinib is reduced associated with

Grade 3 QTcF prolongation, the dose may not be increased. If the dose of quizartinib is reduced associated with Grade 2 QTcF prolongation, the dose may be increased to the dose before dose reduction if QTcF prolongation recovers to Grade 1 or less severe after treatment at a reduced dose for at least 28 days.

If the dose of quizartinib is reduced due to AEs, the dose must not be increased unless the concerned AE recovers to Grade 1 or less severe. If the dose of quizartinib is reduced because concomitant use of a strong CYP3A4 inhibitor is started during the study, quizartinib may be administered at the dose before dose reduction after a 7-day washout when the concomitant use of the strong CYP3A4 inhibitor is discontinued.

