# Grade 2 (QTcF: 481 ms to 500 ms)

- Measure electrolyte levels (K+, Ca++, and Mg++) and supply the electrolytes to ensure recovery to the institutional reference ranges.
- Check concomitant drugs, and discontinue drugs that are known to prolong QTcF, as necessary.
- Reduce the dose of quizartinib by one level. It is not necessary to interrupt treatment.
- The dose may be increased to the dose before dose reduction if QTcF prolongation recovers to Grade 1 or less severe after treatment at the reduced dose for at least 28 days. However, whether prolongation of QT interval occurs or not should be confirmed carefully for the first cycle (28 days) after the dose increase.

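### After a Grade 2 QTcF event at 20 mg/day from about Day 15 onward, the plan sets no minimum time back on drug before the Day 1 rule directs an increase to 30 mg/day

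*Combined protocol and SAP*

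**What the plan says.** Patients on a strong CYP3A4 inhibitor start at 20 mg/day and may go to 30 mg/day (Section 5.2.4.1 and Table 5.2-2).

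**Grade 2 QTcF at 20 mg/day.** Table 5.4-3 allows an interruption of at most 14 days and then: "Resume quizartinib treatment at a dose of 20 mg/day if QTcF prolongation recovers to Grade 1 or less severe". That row says nothing about later increases. The Grade 3 row for patients on a strong inhibitor does: "Do not increase the dose after resumption of quizartinib treatment".

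**Grade 2 QTcF at 30 or 60 mg/day.** Table 5.4-2 lowers the dose one level and allows a return to the earlier dose "if QTcF prolongation recovers to Grade 1 or less severe after treatment at the reduced dose for at least 28 days". Section 5.4.5 repeats this, but it governs increases "in patients whose dose has once been reduced". Section 9.10.2 repeats it after the instruction "Reduce the dose of quizartinib by one level. It is not necessary to interrupt treatment". At 20 mg/day that step does not exist: "If quizartinib is administered at a dose of 20 mg/day, a further dose reduction is not allowed" (Section 5.4).

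**Increase on Day 1 of Cycle 2 or later.** Section 5.2.4.3 states that for non-responders "whose condition before the decision on dose increase satisfies the following requirements, the dose of quizartinib will be increased". The requirements are no related non-hematological toxicity of Grade 3 or worse, a QTcF rise from baseline of no more than 60 ms, and no marrow hypoplasia. A footnote defines one cycle of treatment as 13 consecutive dosing days.

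**Increase on Day 16.** The same section limits increases after an interruption, but only for that decision: "Interruption of treatment for 7 days or longer: The dose will not be increased on Day 16 of Cycle 1".

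**The concern.** The protection is uneven. After a Grade 2 event at 30 or 60 mg/day, a patient spends 28 days at a lower dose before merely returning to the dose at which the event occurred. After a Grade 2 event at 20 mg/day, a patient can be moved above the event dose within days of restarting. The wording is directive, and Section 15.5 allows deviations only for immediate hazards, so an investigator who holds the dose on judgment alone is off protocol.

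QTcF prolongation is the drug's key toxicity. Section 3.2.2 reports a linear relation between AC220 concentration and QTc, and it justifies the Day 16 increase by reading QTc on Day 15, at steady state. A decision made soon after restart loses that justification. Nor is 20 mg/day a low exposure in these patients. Section 3.2.1 estimates a 1.96-fold steady-state AUC with ketoconazole. If exposure is proportional to dose, 20 mg with such an inhibitor resembles 20 × 1.96 = 39 mg alone, and 30 mg resembles 59 mg.

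**Working it through.** The plan gives no figure on this point, so there is none to reproduce. The check has three parts.

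**1. Does any rule impose a wait?** The waits in Table 5.4-2, Section 5.4.5 and Section 9.10.2 all follow a dose reduction, and Section 5.4 rules one out at 20 mg/day. The bar on later increases is written for Grade 3. The interruption limits in 5.2.4.3 apply to Day 16 only. A reading above 450 ms by Day 15 also blocks only the Day 16 increase. That leaves the 13-consecutive-day footnote, which is not tied to the restart:

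- Event on Day 2 or Day 8: 13 consecutive days have not yet been reached, so they must be completed after the restart. The footnote then gives at least 13 days back at 20 mg/day.
- Event on Day 15: the condition is already met, so no minimum applies.

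**2. Time back on drug.** Take an event on Day 15 (that day's dose given), dosing stopped for k days from Day 16, and Day 1 of Cycle 2 on Day 29. Days back at 20 mg/day are 13 − k: 12 days after 1 day off, 6 after 7, and 1 after 12. If the Day 1 visit falls at the end of its window (Day 32), a full 14-day interruption leaves 2 days.

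**3. Exposure at the Day 29 decision.** With half-life h, the fraction of steady state on Day 15 is f15 = 1 − 2^(−15/h). On Day 29 it is

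1 − (1 − f15 × 2^(−k/h)) × 2^(−(13−k)/h).

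Sections 1.2.1.2.5 and 3.2.2 give h of about 3 days, so f15 = 0.969. Doubling to h = 6 days under a strong inhibitor is my assumption, and gives f15 = 0.823.

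| Days off | Days back by Day 29 | h = 3 days | h = 6 days (assumed) |
|---|---|---|---|
| 1 | 12 | 99% | 93% |
| 2 | 11 | 97% | 90% |
| 7 | 6 | 80% | 68% |
| 12 | 1 | 25% | 29% |

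For k = 7 and h = 3: 1 − (1 − 0.969 × 0.198) × 0.25 = 0.798. After 28 days back, even from zero, the figures are 1 − 2^(−28/3) = 99.8% and 1 − 2^(−28/6) = 96%.

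**Illustration.** Take a baseline of 435 ms and 482 ms on Day 15 (a rise of 47 ms, Grade 2), 7 days off and 6 back, h = 3, with QTcF linear in concentration. The drug-related part of the rise on Day 29 is 0.798/0.969 = 0.824 of its Day 15 value.

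- All of the rise drug-related: 435 + 47 × 0.824 = 474 ms.
- Half of it drug-related: 435 + 23.5 + 23.5 × 0.824 = 478 ms.

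Both readings are below Grade 2 and within 60 ms of baseline, so a non-responder who meets the other two requirements is directed to 30 mg/day.

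**The case against.** The strongest reply is that the Day 29 ECG is itself a check. Recovery to Grade 1 needs only 480 ms or less. In the illustration that takes less than a day off drug: 3 × log2(47/45) = 0.2 days if the rise is all drug-related, and 3 × log2(23.5/21.5) = 0.4 days if half is. After 1 to 2 days off, exposure on Day 29 is essentially at steady state and the model predicts 482 to 483 ms. That is Grade 2 again, so Table 5.4-3 calls for another interruption. The 7-day interruption is permitted, but the model does not explain it. This stands: the low-exposure problem belongs to longer interruptions, and 25% is an extreme.

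Other safeguards also stand. The electrolyte and concomitant-drug steps for Grade 2 in Section 9.10.2 name no dose. Follow-up ECGs are required after an interruption, central reading governs dose changes, weekly ECGs follow an increase, and Section 5.7.1 lets the investigator stop treatment. The group is small, because Section 5.6.2.2 says strong inhibitors should be avoided. None of these sets a time back on drug before the increase.

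Three stronger readings are tempting, and the documents support none of them.

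- **The gap extends to 30 and 60 mg/day.** It does not. The 28-day wait is stated three times for those doses, and Section 5.2.4.1 sends dose reductions to Section 5.4.
- **Escalation predictably produces Grade 3 prolongation.** The documents give neither the drug-related share of an individual rise nor dose proportionality below 30 mg (Section 1.2.1.2.5 covers 30 to 90 mg). Projections fall on either side of 500 ms, depending on the assumptions.
- **Any Grade 2 event at 20 mg/day is unprotected.** Events on Day 2 or 8 are protected by the footnote.

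**Conclusion.** The concern holds in a limited form. It applies to a patient at 20 mg/day with no earlier dose reduction (in practice one who started there on a strong CYP3A4 inhibitor) whose Grade 2 event comes at about Day 15 or later and who has not responded. For that patient the plan directs an increase above the event dose with no minimum time back on drug. With an event on Day 15 and a decision on Day 29, that time is 1 to 12 days for interruptions of 12 to 1 days, against 28 days after a Grade 2 event at the higher doses.

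The absence of a wait follows from the text alone. The exposure figures rest on the stated 3-day half-life, with 6 days as an assumed alternative. The QTcF illustration also assumes linearity and a continuing inhibitor.

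The number affected is small and cannot be estimated, because neither the share of patients starting at 20 mg/day nor the Grade 2 rate at that dose is given. Sample size and error rates are unaffected. This is a low-cost safety improvement, not a threat to the trial's conclusion.

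**What to change.** In the Grade 2 row of Table 5.4-3, add that the dose must not be increased until the patient has had at least 28 days of treatment at 20 mg/day after resumption, with QTcF at Grade 1 or less. This matches Table 5.4-2. In Section 5.2.4.3, make the increase on Day 1 of Cycle 2 or later subject to Section 5.4.1.

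The change needs no extra visits or patients. Its cost is delay. After an event on Day 15 and 1 to 12 days off, restart falls on Day 17 to 28, and 28 days of dosing end on Day 44 to 55. If decisions are made on Day 1 of a cycle, the increase moves from Day 29 to Day 57. Day 1 of Cycle 4, the latest per-patient date in the data cut-off rule of Section 11.4.3, is Day 85. Time at 30 mg/day before it therefore falls from 85 − 29 = 56 days to 85 − 57 = 28 days, in patients with refractory or relapsed disease.

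If that is judged too long, the minimum that meets the concern is about 15 days, the time to steady state given in Section 3.2.2. It would end on Day 31 to 42, so it saves time mainly if an increase between cycle starts is allowed. With an assumed 6-day half-life, 15 days from zero reaches only 82% of steady state.
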